The study is expected to last approximately 120 days from the start of the intervention to the completion of the active intervention period for participants in wave 2. Final data collection will continue until all participants have been debriefed to ensure accurate documentation of participation status and any withdrawal requests.

Participants' time commitment will vary based on their study condition and actions taken. Estimates of individual participation time by assigned condition and action taken are presented in the table below:

Group	Action taken	Read	Book	Attend	Receive	Total
		reminder	appointment	appointment	debrief	time
Control group	Do not book or attend an	-	-	-	5 mins	5 mins
	appointment					
	Book, but do not attend	-	20 mins	-	5 mins	25
	appointment					mins
	Book & attend	-	20 mins	60 mins	5 mins	85
	appointment					mins
Intervention	Do not book or attend an	5 mins	-	-	5 mins	10
group	appointment					mins
	Book, but do not attend	5 mins	20 mins	-	5 mins	30
	appointment					mins
	Book & attend	5 mins	20 mins	60 mins	5 mins	90
	appointment					mins

Total Number of Participants and Sites

This is a single-site study conducted at Centretown Community Health Centre (CCHC). The study will include a randomly selected subsample (N = 330) of eligible individuals listed in the Community Diabetes Education Program of Ottawa (CDEPO) patient database at CCHC. Participants will be randomly allocated 1:1 to either an intervention or control arm (165 per arm). To support clinic capacity, intervention participants will receive reminders in two waves. Control participants will be matched to these waves to ensure comparable observation periods. This sample size achieves 80% power to detect a 10% difference in the primary outcome of screening attendance between the groups (or a proportion of 0.03 in the control arm versus 0.13 in the intervention arm), using a two-sided Z-test with pooled variance at a 5% significance level. Some attrition is anticipated due to outdated contact details or death; thus, our calculation accounts for approximately 10% attrition.

Study Enrollment and Withdrawal

Eligible participants listed on the CDEPO database (i.e., clients with existing medical charts in the CCHC's Electronic Medical Records (EMR), housed on PS Suite v. A-5.24.204, a certified EMR system

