We will use random number generation to assign a condition (control or reminder) to a client at the CCHC. Specifically, the CCHC member responsible for data management will share a CSV file containing unique client ID codes of all eligible individuals. Then the OHRI statistician (MT, BY) will conduct the randomization schedule below, through creating a randomized list of eligible individuals in a spreadsheet containing unique participants IDs. Once the file is prepared, the statistician will lock columns in the document to prevent errors and send the locked document to the CCHC. The document will be stored in an encrypted, limited access folder on the CCHC network. The unlocked columns of the spreadsheet will be used to track whether the client responded to the reminder and other study variables (see below for example spreadsheet). When the data is sent to the OHRI post-

trial, the client ID column will be removed and replaced by "Participant 1- ..." before sharing to clear the document of direct identifiers.

RANDOMIZATION SCHEDULE

- 1) 330 participants randomly selected from all eligible individuals listed in the Community Diabetes Education Program of Ottawa (CDEPO), registered at Centretown Community Health Centre (CCHC).
- 2a) 330 eligible participants randomly assigned to control (n = 165) or intervention (n = 165)
- 2b) Participants control and intervention groups should be balanced across age and date of last chart update
- 3a) Control group randomised into wave 1 and wave 2 (n= 80; 81)
- 3b) Intervention group randomised into wave 1 and wave 2 (n= 80; 81)

Statistical Considerations

Study Hypotheses

- Linguistically tailored reminders will significantly increase DRS appointment attendance (primary outcome) compared to no reminder.
- Linguistically tailored reminders will significantly increase DRS appointment booking compared to no reminder.

Sample Size Determination

Sample size calculations are based on a minimum effect estimate of 10% (based on the effective sizes usually detected in DRS trials¹⁸) and to achieve 80% power, which requires a total sample of 250 participants. To achieve this sample size, we have estimated we will need to randomize 330

individuals registered to the CDEPO program at CCHC to account for approximately 30% attrition due to outdated contact details or death.

Statistical Methods

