All analyses will be conducted according to the intention to treat principle. Descriptive statistics (mean and SD for continuous variables or median and IQR for skewed distributions, and frequency and proportion for categorical variables) will be used to summarize participant characteristics in each arm. For the primary analysis of the primary outcome, we will compare screening attendance between the arms using absolute and relative difference between two proportions with 95% confidence intervals and assess the statistical significance of the difference using a chi-squared test. If the large-sample assumptions are not met, Fisher's exact test will be used. Statistical significance will be assessed at the 5% level. A similar statistical approach will be used for secondary outcomes. For the final objective of assessing effect modification, we will use logistic regression analysis with the treatment arm, effect modifier and the interaction between treatment arm and effect modifier in the model. Least square mean differences from the model will be used to compare the outcome differences between the subgroup variables: 1) Age, 2) Gender/Sex 3) Preferred Language, 4) Prior DRS Record 5) FSA (Forward Sortation Area).

Source Documents and Access to Source Data / Documents

Access to study records will be limited to REB-approved members of the study team. The PI will permit study-related monitoring, audits, and inspections by the REB and/or OHRI and compliance and Version date: 04/06/2025

quality assurance groups of all study related documents (e.g. source documents, data collection instruments, study data etc.). The PI will ensure the capability for inspections of applicable study-related facilities (e.g. pharmacy, diagnostic laboratory, etc.). Please see the data management plan for more information about data access.

Study Oversight

The study will be overseen by the primary investigator, ([name]) and his delegate ([name]) who will ensure data safety protocols are in place and followed by OHRI and CCHC site data handlers. Data safety during reminder testing phase involves the protection of CCHC client identities when sharing data. No identifying information (i.e., name, health card number, address, phone number or email address) will ever be sent to the OHRI team. If a breach were to occur, the study would stop until the breach was resolved and then restart once there is no question of a second breach.

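### Failed delivery and death are budgeted as lost sample size, but under the planned intention-to-treat analysis these people stay in the denominator, so the stated basis for 80% power does not match the analysis

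*Protocol*

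**What the plan says.** Two sections of the protocol describe the sample size.

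- *Total Number of Participants and Sites*: 165 per arm. "This sample size achieves 80% power to detect a 10% difference in the primary outcome of screening attendance between the groups", specified as "a proportion of 0.03 in the control arm versus 0.13 in the intervention arm" and tested "using a two-sided Z-test with pooled variance at a 5% significance level". The section says the calculation allows for about 10% attrition from outdated contact details or death.
- *Sample Size Determination*: 80% power for a 10-point effect "requires a total sample of 250 participants", raised to 330 "to account for approximately 30% attrition due to outdated contact details or death".

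The analysis is set out in *Statistical Methods*: "All analyses will be conducted according to the intention to treat principle". Under *Study Procedures / Evaluations*, bookings and attendance are logged by clinic staff in a tracker inside the electronic medical record, so the outcome needs no contact with the participant. The only removals described are withdrawal by the participant and termination by an investigator, by study discontinuation or by the ethics board (*Participant Withdrawal or Termination*). No section removes someone because a reminder failed or because they died.

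**The concern.** Raising a sample size for attrition is right when the people concerned have no outcome and drop out of the analysis. Here they have one. Someone with a dead email address can still book and attend unprompted, and the tracker will show whether they did. Someone who dies is recorded as not attending. Both remain in the arm to which they were randomised.

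A failed reminder therefore pulls the intervention arm's attendance towards the control rate. The allowance in the protocol protects against a smaller n, which these causes do not produce, and not against a smaller difference, which failed delivery does produce. The quoted 80% therefore belongs to an analysis other than the planned one.

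Calling these people attrition also leaves it unclear whether they stay in the denominator. In the intervention arm a failed reminder can show on Day 1 or Day 30. Controls are sent nothing until Day 121 or Day 151. Any exclusion based on delivery would rest on information gathered differently in the two arms.

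**Working it through.** **Inputs.** Control 0.03, intervention 0.13, two-sided 5%, pooled Z-test, 80% power, 165 per arm (*Total Number of Participants and Sites*). Base 250, loss 30%, total 330 (*Sample Size Determination*). Loss 10% for the same causes and the same total (*Total Number of Participants and Sites*).

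**Formulas.** With p̄ = (p1 + p2)/2 and n per arm:

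- SE0 = √[2p̄(1 − p̄)/n]
- SE1 = √[(p1(1 − p1) + p2(1 − p2))/n]
- Power = Φ[(p2 − p1 − 1.96 × SE0)/SE1]

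**Step 1: reproduce the plan.** For 0.03 against 0.13, 80% power needs 115 per arm, 230 in total. Then 230/0.70 = 328.6, or 329, which agrees with 330. In reverse, 330 × 0.70 = 231, about 115 per arm, with SE0 = 0.0358 and SE1 = 0.0352. Power = Φ[(0.10 − 0.0701)/0.0352] = Φ(0.85) = 80.2%. So 80% with 30% loss is reached by taking the 30% out of the denominator.

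The stated base of 250 does not lead to 330 at either loss figure: 250/0.70 = 358 and 250/0.90 = 278. Going from 250 to 330 implies 1 − 250/330 = 24%.

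**Step 2: everyone kept, 0.13 is the whole-arm rate.** n = 165, SE0 = 0.0299, SE1 = 0.0294. Power = Φ[(0.10 − 0.0585)/0.0294] = Φ(1.41) = 92.1%.

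**Step 3: everyone kept, 0.13 is the rate among those reached.** Assume that people whose reminder fails attend at the 3% control rate. With a fraction d undelivered, the intervention-arm rate is 0.03 + 0.10(1 − d).

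| Undelivered | Intervention arm | Difference | Power at 165 per arm |
|---|---|---|---|
| 0% | 0.130 | 10.0 points | 92.1% |
| 10% | 0.120 | 9.0 points | 87.7% |
| 20% | 0.110 | 8.0 points | 81.6% |
| 24.2% | 0.106 | 7.6 points | 78.4% |
| 30% | 0.100 | 7.0 points | 73.4% |

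At 30%: SE0 = 0.0271, SE1 = 0.0269, and Φ[(0.07 − 0.0532)/0.0269] = Φ(0.63) = 73.4%. Power crosses 80% at about 22% undelivered. Exact power at 30% is 75.3% for the uncorrected chi-squared test and 67.9% for Fisher's test.

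**Step 4: deaths.** Give the deceased zero attendance in both arms. With 25% undelivered and 5% deaths, power is about 74.3%. If all 30% were deaths (0.021 against 0.091), power is 79.2%. The protocol gives no split between the two causes.

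**The case against.** The strongest reply is that the protocol states 0.13 for the intervention arm and the 10 points as a difference between the groups. Read literally, these are arm-level figures that already include non-delivery, and power is then 92%, so the plan is conservative. This stands as one possible reading. It does not rescue the reasoning, because on that reading an allowance for outdated contact details is not needed at all.

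A second reply is that the shortfall depends on the 30% figure, which the protocol's own 10% contradicts. This also stands: at 10% or 20% undelivered, power is above 80% on either reading of 0.13.

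A reader might go further than the documents allow in three ways.

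- **That the trial is underpowered.** This needs 0.13 to be the rate among those reached and more than about 22% non-delivery. The protocol establishes neither.
- **That every undelivered participant counts as a non-attender.** They can attend unprompted, which is why the working gives them 3%.
- **That the team intends to exclude undelivered cases from one arm.** No section proposes this, and intention to treat is stated for all analyses. Control-arm delivery failures may also come to light from Day 121 or Day 151, before data transfer.

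Finally, some loss of n is real. Consent is waived, and participants may withdraw their data after debriefing. The attrition sentences do not name that cause, and the protocol gives no rate for it.

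**Conclusion.** The stated justification for 330 does not match the stated analysis. The 80% figure at 30% loss holds if undelivered and deceased participants leave the denominator, whereas intention to treat with a chart-based outcome keeps them in. This mismatch follows from the protocol's own text and arithmetic.

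Its effect on power is conditional. At 165 per arm, power is about 92% if 0.13 is a whole-arm rate. If 0.13 applies to those reached, it is about 88% at 10% undelivered, 82% at 20% and 73% at 30%. Part of the 30% being deaths would raise the last figure somewhat, to at most 79%. These results assume a 3% control rate, 3% attendance among people whose reminder fails, and no data withdrawals. The documents support neither a finding that power is inadequate nor a finding that 80% fails on every reading.

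**What to change.** 1. Reconcile the 10% and 30% loss figures, and the base of 250 with them, so that both sections give one calculation.
2. State whether 0.13 is the expected rate in the whole intervention arm or among people who receive the reminder.
3. Replace the attrition sentence with power under dilution at the chosen rate. For example: *If a proportion of reminders is not delivered and those participants attend at the control rate, a 10-point effect among those reached becomes 9 points at 10% non-delivery (power 88%) or 7 points at 30% (power 73%), with 165 per arm.* If 0.13 is the whole-arm rate, state about 92% and drop the allowance for non-delivery.
4. State that participants with undelivered reminders and those who die remain in the denominator of their randomised arm. Data withdrawals are removed as the withdrawal and data-extraction sections require, and counted by arm.
5. Where charts already show a death or an invalid email address, remove them at Day 0 before random selection, so that the step applies equally to both arms. This will not catch addresses that fail only on sending.

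The cost is a few sentences and a chart check before selection. The trial does not have to be enlarged. The price is that the stated power may be less favourable than 80% if the team stands by 30% and by a rate among those reached.

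### With about five control attendees expected, the interaction models for preferred language and postal area will probably contain empty cells, leaving some log-odds contrasts with no finite estimate

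*Protocol*

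**What the plan says.** The Secondary Objectives table of the protocol makes effect modification a secondary objective. It is to be measured by interactions between arm and each of age, gender/sex, preferred language, prior screening and FSA in a logistic model for attendance. Statistical Methods gives the method, in near-identical words in two paragraphs: "we will use logistic regression analysis with the treatment arm, effect modifier and the interaction between treatment arm and effect modifier in the model". It continues: "Least square mean differences from the model will be used to compare the outcome differences between the subgroup variables".

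The planning rates are in Total Number of Participants and Sites: "a proportion of 0.03 in the control arm versus 0.13 in the intervention arm", with 165 participants per arm.

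The Intervention Phase section offers the reminder in four languages. The trial tracker records the client's spoken language without limiting the options, and records FSA as the first three characters of the postal code. No grouping of languages or FSAs is stated. Statistical Methods gives the comparison of proportions an exact-test fallback for small counts, but gives the interaction models none.

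**The concern.** With a categorical modifier, a model containing arm, modifier and their interaction is saturated: every arm-by-level cell has its own log-odds. If nobody in a cell attends, that log-odds is minus infinity, and so is every contrast that uses it. Software then either fails to converge or prints a very large coefficient with an enormous standard error. If the empty cell belongs to the reference level, all the interaction terms are affected.

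The language result is the one most at stake, because the trial's stated purpose concerns linguistic minority groups. If levels were merged only after the empty cells had been seen, the definition of the moderator would depend on the data.

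**Working it through.** **Inputs.** From Total Number of Participants and Sites: attendance 0.03 (control) and 0.13 (intervention), 165 per arm. From Intervention Phase: four reminder languages, taken as the minimum number of levels. Assumed, because the protocol does not give them: the language mix, and an FSA count of five to ten or more.

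**Plan's own figure.** "This sample size achieves 80% power to detect a 10% difference in the primary outcome of screening attendance between the groups", "using a two-sided Z-test with pooled variance at a 5% significance level". With pooled rate 0.08:

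n per arm = [1.96√(2×0.08×0.92) + 0.8416√(0.03×0.97 + 0.13×0.87)]² / 0.10² ≈ 114.4, so 115 per arm and 230 in total.

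230/0.70 = 329, which agrees with the 330 stated if attrition is 30%. The planning rates are therefore the right basis for this check.

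**Expected attendees.** Control: 165 × 0.03 = 4.95 (95% binomial range 1 to 10). Intervention: 165 × 0.13 = 21.45. The control arm is the limiting one.

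**Chance of an empty control level.** If a set of levels S holds share s of participants, the chance that none of its members attends is (1 − 0.03s)^165. Inclusion-exclusion over the levels gives the chance that at least one is empty.

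- Two levels, 50/50: 2×0.0826 − 0.0066 = 0.159.
- Two levels, 80/20: 0.3705 + 0.0182 − 0.0066 = 0.382 (0.39 when intervention cells are counted too).
- Four equal levels: 4×0.2888 − 6×0.0826 + 4×0.0234 − 0.0066 = 0.746.
- Five equal levels: 5×0.3705 − 10×0.1364 + 10×0.0499 − 5×0.0182 + 0.0066 = 0.903.
- Ten equal levels: the expected number of empty control levels is 10×0.997^165 = 10×0.609 = 6.1, and the chance of at least one is about 100%.

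Simulation (40,000 trials per scenario, no true moderation) agrees:

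| Modifier (assumed mix) | At least one empty control level, 165 per arm | 125 per arm |
|---|---|---|
| Binary 50/50 | 16% | 28% |
| Language, 4 equal | 75% | 86% |
| Language, 40/30/20/10 | 84% | 91% |
| Language, 70/10/10/10 | 94% | 97% |
| FSA, 5 equal | 90% | 96% |
| FSA, 8 equal | 99.8% | about 100% |
| FSA, 10 equal | about 100% | about 100% |

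The second column is shown because Sample Size Determination plans for 250 evaluable participants, or 125 per arm. The protocol states attrition in two ways: "our calculation accounts for approximately 10% attrition" in one section, and about 30% in the other. Either makes the cells sparser.

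**What an ordinary fit does.** One simulated trial with four languages had no control attendee among 67 participants in one language and none among 34 in another. Maximum likelihood gave an arm coefficient of 22.8 and interaction coefficients of −20.6, 0.55 and −21.9. The standard errors ran from about 16,000 to 28,000.

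**Continuous age.** In 300 simulated trials with age as a linear modifier, 0.3% of fits failed.

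**Sensitivity to the control rate.** At 8% control attendance, the chance of an empty control level falls to 14% for four equal languages but is still 96% for ten FSAs.

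**The case against.** The strongest reply is that the protocol names logistic regression without specifying maximum likelihood, Wald tests, raw FSA codes or ungrouped languages. A statistical analysis plan could group levels and use a penalised or exact method without contradicting the quoted sentence. That is fair as far as it goes. But the protocol is not silent here. It names the moderators, the model and the contrast to be reported, and it gives a small-count fallback for the proportions but none for models that split the same events much further. Read in the usual way, the stated method breaks down at the plan's own rates.

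Four stronger readings are tempting, and the documents do not support them.

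- **That none of the five moderation analyses can be estimated.** Continuous age is essentially safe, and sex and prior screening will usually be estimable unless very unevenly split.
- **That any moderation reported would be an artefact.** The likelihood-ratio interaction test stays finite when cells are empty. In 4,000 simulated trials per scenario with no true moderation, it rejected at a nominal 5% in 6.3% of trials with four equal levels, 4.9% with a 55/20/15/10 split and 3.4% with ten equal levels. The failure lies in the log-odds estimates and Wald inference.
- **That the least-squares differences are on the wrong scale.** The protocol names no scale. Back-transformed values in a saturated model are simply the observed proportions, finite even at zero events, although their Wald intervals are not usable.
- **That the objective is presented as confirmatory.** The synopsis speaks of exploring moderation, and Study Hypotheses contains none on it. The protocol also claims no power for these tests, so low power is a separate and general matter.

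**Conclusion.** The concern holds for two of the five moderators. At 3% control attendance and 165 per arm, at least one control level without attendees is very probable for language (about 75-95% with four levels) and almost certain for FSA (about 90% with five levels, about 100% with ten). The affected log-odds interaction terms and least-squares differences would have no finite estimate, and their Wald intervals and p-values could not be used. Binary moderators carry a smaller risk, about 15% at 50/50 and about 40% at 80/20.

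These figures rest on the protocol's planning rates and on an assumed language mix and FSA count. Higher control attendance would largely rescue language but not a many-level FSA. One exploratory secondary objective is affected; the primary comparison is not.

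**What to change.** Before the data leave the clinic, amend Statistical Methods or settle the following in the analysis plan:

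1. Define a small number of language levels and one coarse FSA grouping, chosen without sight of attendance, or drop FSA as a moderator.
2. Keep age continuous.
3. Fit Firth-penalised logistic regression with arm, modifier and interaction, and test the interaction by penalised likelihood ratio.
4. Report attendance proportions by arm within each level, and risk differences with score-type intervals, which remain usable when a cell has no attendee.

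The cost is some wording and a standard software option. The real downside is coarser moderators. Merging languages, for example into English against all others, would hide differences among the French, Arabic and Mandarin versions, so the grouping should be a deliberate choice. Penalisation makes the estimates finite but adds no information, and the intervals will stay wide.
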